9.5.4 Dose Modifications and Mitigation Plan for Ocular Adverse Events

Events of conjunctivitis and keratitis have been reported in patients treated with tisotumab vedotin. To prevent occurrence and ensure appropriate handling, events should be prevented and managed as described below.

Ocular toxicity mitigation plan

Ocular toxicity mitigation plan

Preventive measures for all patients:

- Use of preservative-free lubricating eye drops from the start of trial treatment until the end of treatment.
- Avoid use of contact lenses while treated with tisotumab vedotin.
- Use of refrigerator-based eye cooling pads during infusion, e.g. THERA PEARL Eye Mask or similar. To be applied immediately before infusion in accordance with the instructions provided with the eye cooling pads.
- Administration of local ocular vasoconstrictor before infusion (brimonidine tartrate 0.2% eye drops or similar, 3 drops in each eye immediately prior to start of infusion; otherwise to be used in accordance with the product prescribing information). If the patient does not tolerate ocular vasoconstrictors due to adverse reactions, continued treatment with these may be stopped at the discretion of the investigator and following discussion with the Genmab Medical Officer.
- Application of steroid eye drops for 3 days from the day of infusion (dexamethasone 0.1% eye drops or equivalent, 1 drop in each eye 3 times daily for 3 days [first drop to be given before start of infusion], otherwise to be used in accordance with the product prescribing information).

Grading: All ocular events of should be graded according to both:

- Ophthalmological grading based on the objective eye-examination findings performed by the ophthalmologist.
- CTCAE grading system based on National Cancer Institute (NCI) CTCAE version 4.03 ([NCI-CTCAE v4.03, 2010](#)) assessed by the investigator.

Conjunctivitis should be handled according to the following instructions (based on CTCAE grading)

Conjunctivitis grade 1	Hold dosing until the event is managed effectively by topical treatment initiated by the ophthalmologist (according to treatment guidelines below). When the event is managed effectively the patient can be re-treated with the same dose of trial drug as being administered prior to the event onset.

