First occurrence of conjunctivitis grade 2	Hold dosing. Topical treatment should be initiated by the ophthalmologist (according to treatment guidelines below). When the event has improved to grade ≤ 1 , dosing of trial drug can be resumed at a reduced dose (please refer to dose modification scheme below).
Second occurrence of conjunctivitis grade 2	Hold dosing and topical treatment should be initiated by the ophthalmologist (according to treatment guidelines below). When the event is grade ≤ 1 , dosing of trial drug can be resumed at a further reduced dose

Ocular toxicity mitigation plan	
	(please refer to dose modification scheme below).
≥ 3rd occurrence of conjunctivitis grade 2	Hold dosing and topical treatment should be initiated by the ophthalmologist (according to treatment guidelines below). When the event is grade ≤ 1, dosing of trial drug should not be further reduced but resumed at 0.9 mg/kg.
First occurrence of conjunctivitis grade ≥ 3	Hold dosing. Topical treatment should be initiated by the ophthalmologist (according to treatment guidelines below). When the event has improved to grade ≤ 1, dosing of trial drug can be resumed at a reduced dose (please refer to dose modification scheme below).
Second occurrence of conjunctivitis grade ≥ 3 (despite dose reduction)	Permanently discontinue treatment with trial drug.
> 2nd occurrence of conjunctivitis grade > 3	Permanently discontinue treatment with trial drug.
Keratitis should be handled according to the following instructions (based on CTCAE grading)	
First occurrence of keratitis grade ≤ 2	Hold dosing until the event is managed effectively by topical treatment (according to treatment guidelines below) initiated by the ophthalmologist. When the event is ≤ grade 1, dosing of trial drug can be resumed at a reduced dose (please refer to dose modification scheme below).
Second occurrence of keratitis grade ≤ 2	Hold dosing and topical treatment (according to treatment guidelines below) should be initiated by the ophthalmologist. When the event is grade ≤ 1, dosing of trial drug can be resumed at a further reduced dose (please refer to dose modification scheme below).
Third occurrence of keratitis grade ≤ 2 (despite dose reductions)	Permanently discontinue treatment with trial drug.
Keratitis grade ≥ 3	Permanently discontinue treatment with trial drug.
Conjunctival ulceration should be handled according to the following instructions (based on CTCAE grading)	

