If an ophthalmological evaluation reveals fluorescent patches or conjunctival ulceration of any grade	Hold dose until conjunctivitis/conjunctival ulceration is managed effectively by topical treatment (according to treatment guidelines below). When the event is managed effectively, dosing of trial drug can be resumed at a reduced dose (please refer to dose

Ocular toxicity mitigation plan	
	modification scheme below). If symptoms do not stabilize/improve after dose reduction, the patient must permanently discontinue treatment with trial drug.
Other Eye Toxicity should be handled according to the following instructions (based on CTCAE grading)	
Ophthalmological evaluation reveals conjunctival/corneal scarring	Permanently discontinue treatment with trial drug.
Any grade of symblepharon	Permanently discontinue treatment with trial drug.
Any dose delay related to ocular toxicity exceeding 12 weeks	Permanently discontinue treatment with trial drug following discussion with the Genmab Medical Officer.

Treatment guidelines

Ocular symptom	Treatment guideline (The length of treatment should be decided by the local ophthalmologist)
Conjunctivitis: CTCAE grade 1	The local ophthalmologist should prescribe frequent dosing of preservative-free topical steroid drops
Conjunctivitis: CTCAE grade 2	The local ophthalmologist should prescribe frequent dosing (every 2nd hour) of preservative-free topical steroid drops in conjunction with preservative-free antibiotic prophylaxis such as chloramphenicol
Conjunctivitis: CTCAE grade 3	The local ophthalmologist should prescribe frequent dosing (every 2nd hour) of preservative-free topical steroid drops in conjunction with preservative-free antibiotic prophylaxis such as chloramphenicol
Keratitis: CTCAE grade 1	The local ophthalmologist should prescribe frequent dosing of preservative-free topical steroid drops
Keratitis: CTCAE grade 2	The local ophthalmologist should prescribe frequent dosing (every 2nd hour) of preservative-free topical steroid drops in conjunction with preservative-free antibiotic prophylaxis such as chloramphenicol
Conjunctival ulceration: any grade	The local ophthalmologist should prescribe frequent dosing (every 2nd hour) of preservative-free topical steroid drops in conjunction with preservative-free antibiotic prophylaxis such as chloramphenicol

Dose modification scheme:

Previous dose of tisotumab vedotin	Reduced dose of tisotumab vedotin
---	--

2.0 mg/kg	1.3 mg/kg
1.3 mg/kg	0.9 mg/kg

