10.1.7 Ophthalmological Evaluation

Ophthalmological evaluations should be performed at screening and during the trial as indicated in the trial flow chart.

The ophthalmological evaluation should include collection of medical ophthalmological history (at screening only), visual acuity assessment, Shirmer's test, slit-lamp examination, measurement of ocular pressure and funduscopy.

Patients experiencing ocular symptoms during the trial must be referred to an ophthalmologist for prompt review (preferably within 72 hours and no later than within one week).

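### Protocol 9.5.4 gives two different restart doses for grade 1 conjunctivitis with fluorescent patches or conjunctival ulceration, and does not say which row governs

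*Protocol*

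**What the plan says.** The ocular mitigation table in Protocol Section 9.5.4 has seven conjunctivitis rows, defined by CTCAE grade and occurrence number. In the grade 1 row, dosing is held until topical treatment started by the ophthalmologist is effective; after that, "the patient can be re-treated with the same dose of trial drug as being administered prior to the event onset".

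A later block covers conjunctival ulceration. Its trigger is an examination finding, not a conjunctivitis grade: "If an ophthalmological evaluation reveals fluorescent patches or conjunctival ulceration of any grade". Its action begins "Hold dose until conjunctivitis/conjunctival ulceration is managed effectively by topical treatment" and continues "When the event is managed effectively, dosing of trial drug can be resumed at a reduced dose". It then adds a stop rule: "If symptoms do not stabilize/improve after dose reduction, the patient must permanently discontinue treatment with trial drug".

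The reduced dose is read from the scheme at the end of the section: 2.0 goes to 1.3 mg/kg, 1.3 goes to 0.9 mg/kg, and 0.9 mg/kg is not reduced further.

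Section 9.5.4 also requires every ocular event to be graded twice, once on the ophthalmologist's objective findings and once by CTCAE. SAP Section 4.5 refers back to Protocol Section 9.5 for dose reductions and adds no rule of its own.

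**The concern.** The eye-examination row is not limited by the grade of any accompanying conjunctivitis, and its action names conjunctivitis alongside ulceration. It therefore reaches patients who also sit in a conjunctivitis row. For grade 1 the two rows lead to different doses, and no sentence says which applies.

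Two sites that each follow a row as written could restart similar patients at different doses. Ocular events are adverse events of special interest (Protocol Section 11.1.3) within the primary endpoint of adverse events, so this is a patient-safety matter first. It also reaches the data: the dose-adjusted field, actual dose and cumulative dose in the exposure listing (SAP Section 11.1) and action taken in the adverse event listing (SAP Section 11.2) would partly reflect which row a site used. In addition, Protocol Section 11.3.2 defines overdose by reference to the dose that the protocol specifies. Where two rows specify different doses, it is unclear whether the higher one would be reportable.

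**Working it through.** No sample size, error rate or event count bears on this point. The check is a side-by-side reading of the rows, plus the arithmetic of the dose scheme.

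**Step 1. Can one patient meet both rows?** Yes.
- The eye-examination row carries no conjunctivitis grade or occurrence limit, and its action covers conjunctivitis.
- The grade 1 row has the ophthalmologist start treatment, so an eye examination is expected.
- Protocol Section 10.1.7 sends patients with ocular symptoms to an ophthalmologist and lists the content of the evaluation as "visual acuity assessment, Shirmer's test, slit-lamp examination, measurement of ocular pressure and funduscopy", in addition to ophthalmological history at screening. The slit-lamp examination gives an opportunity to record such findings.
- The dual grading rule means that an examination-based row and a CTCAE-based row can both attach to one event.

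**Step 2. Do the rows differ for grade 1?** The hold condition is the same in both: effective topical management. Only the restart dose differs. With relative gap = 1 − (reduced dose / same dose):

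| Dose before event (mg/kg) | Grade 1 row | Eye-examination row | Gap |
|---|---|---|---|
| 2.0 | 2.0 | 1.3 | 1 − 1.3/2.0 = 35.0% |
| 1.3 | 1.3 | 0.9 | 1 − 0.9/1.3 = 30.8% |
| 0.9 | 0.9 | 0.9 | 0% |

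**Step 3. Do the rows differ for the other conjunctivitis rows?**

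| Conjunctivitis row | Its action | Against the eye-examination row |
|---|---|---|
| Grade 2, first or second occurrence; grade ≥ 3, first occurrence | Resume at the next reduced dose once grade ≤ 1 | Same dose step; the hold test is worded differently |
| Grade 2, third or later occurrence | Resume at 0.9 mg/kg once grade ≤ 1 | Same dose for a patient already at 0.9 mg/kg |
| Grade ≥ 3, second occurrence, and the later-occurrence row | Permanent discontinuation | A permission to resume, with its own stop clause |

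**Step 4. Does any text rank the rows?** None was found.
- Protocol Section 8.5.3.1 makes unacceptable toxicity under Section 9.5 a reason to discontinue, which helps with stop rules but says nothing about a restart dose.
- The opening of Section 9.5 allows discretionary reduction after agreement with the sponsor's medical officer and sets no order between rows.
- SAP Section 4.5 only points back to Section 9.5.

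**The case against.** The best defence is that the eye-examination row is the specific rule. It has its own heading, is triggered by a specific finding and names conjunctivitis in its action. A reader could take it to displace the grade 1 row whenever that finding is present. Both rows also use permissive wording, so neither strictly mandates a dose. This is a reasonable inference, but the table does not state it. The grade 1 row contains no exception for an examination finding, and a site that follows it as written could restart at a dose the other row does not provide for.

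A second defence is that the effect is contained. About 25 patients are expected, all endpoints are listed only, and the exposure listing shows each dose and the reason for any adjustment. No planned estimate would be biased, and inconsistent handling would be visible. That limits the statistical consequence but does not settle the instruction to sites. The 24-hour reporting route in Protocol Section 11.3.1 covers non-serious ocular events from grade 2 upward. It would not by itself catch a non-serious grade 1 conjunctivitis, although an accompanying ulceration graded 2 or higher in its own right would be reported.

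Three stronger readings are tempting, and the documents do not support them as firm contradictions:
- **Stop against resume.** A reader might infer that the row headed "Second occurrence of conjunctivitis grade ≥ 3 (despite dose reduction" collides with the eye-examination row, since one stops treatment and the other allows it to resume. But the first is an order and the second a permission, and Protocol Section 8.5.3.1 can be read as making any Section 9.5 stop sufficient. A patient back at grade ≥ 3 after a reduction may also meet the eye-examination row's own stop clause.
- **Different hold tests.** Improvement to grade ≤ 1 and effective management can both be required and both be met.
- **Third or later grade 2 event.** A reader might infer the reverse conflict, with the conjunctivitis row resuming and the eye-examination row stopping. But the first resumes only after improvement to grade ≤ 1, while the second stops only when symptoms fail to stabilize or improve. For one event these conditions largely exclude each other.

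**Conclusion.** The point holds for one patient state: CTCAE grade 1 conjunctivitis with fluorescent patches or conjunctival ulceration, in a patient at 2.0 or 1.3 mg/kg. The two applicable rows give restart doses that differ by 35% or 31%, and neither document says which governs. At 0.9 mg/kg the rows agree.

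This rests on reading the eye-examination row as its trigger and action are written, that is, without a limit by conjunctivitis grade. How often the finding accompanies grade 1 conjunctivitis is not given, so the number of patients affected cannot be estimated. The point does not extend to a claim that the table tells sites both to stop and to resume treatment. It is a conflict between two stated dosing instructions for an event of special interest. It should be reconciled, although it threatens no planned analysis.

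**What to change.** The sponsor's medical team should reconcile the conjunctivitis rows with the eye-examination row in Protocol Section 9.5.4. One sentence in the table should state which row governs the restart dose when a CTCAE-graded conjunctivitis and the eye-examination finding are present together. The same sentence can confirm how the hold conditions and the permanent-stop instructions combine, which would also close off the weaker readings. Both the conjunctivitis block and the ulceration row should refer to it. The choice of rule is clinical and belongs to the sponsor; no view is taken here.

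The cost is a small protocol amendment and a site training update. No extra visits or data are needed, and the SAP needs no change because it already defers to Section 9.5.

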9.5.5 Dose Modification for QTcF Changes in the Electrocardiogram

Prolongation of QTcF interval during the trial should be managed as follows:

- For CTCAE grade 1 QTcF interval prolongation (450 to 480 msec): check electrolytes (calcium, magnesium and potassium) prior to next dosing, but no dose adjustment or dosing hold is required.
- For CTCAE grade 2 QTcF interval prolongation (481 to 500 msec): hold dosing until improvement to grade 1 or lower and check electrolytes (calcium, magnesium and potassium) and substitute until normal levels; then dose can be restarted and electrocardiograms (ECGs) should be performed at least every other day.

If the QTcF interval prolongation is not related to electrolyte abnormality, hold dosing until improvement to grade 1 or lower; then next infusions may be restarted at half of the initial infusion rate; ECGs should be performed at least every other day.

- For CTCAE grade 3 QTcF interval prolongation (≥ 501 msec on at least two separate ECGs): stop dosing. Then, check electrolytes (calcium, magnesium and potassium) and substitute until normal levels; ECGs should be performed at least daily; consider obtaining cardiology consult.

9.5.6 Dose Modification for Increased Liver Enzymes

In case of CTCAE grade ≥ 3 liver enzymes increase is not resolved (decreased to grade 2 or lower) at time of dosing, the site must contact Genmab Medical Officer before the next dosing of the patient, in order to decide whether there should be any dose adjustment, delay or withdrawal of the patient.

9.5.7 Precautions

Patients receiving the following therapy three weeks after the last treatment with tisotumab vedotin should be monitored closely for adverse reactions:

- Drugs and substances known to be strong cytochrome P450 3A4 (CYP3A4) and P-glycoprotein (P-gp) inhibitors (e.g., amiodarone, boceprevir, clarithromycin, conivaptan, grapefruit juice, indinavir, itraconazole, ketoconazole, lopinavir/ritonavir, mibefradil, nefazodone, nelfinavir, posaconazole, saquinavir, telaprevir, telithromycin, verapamil, voriconazole) should not be administered during the trial period.

9.6 Prior and Concomitant Therapy

Any medication or therapy other than tisotumab vedotin is considered concomitant medication and should be recorded in the eCRF with the following information:

- Start date
- Route of administration
- Stop date of administration or ongoing at trial termination
- Indication/reason for use
- The total daily dose should be filled in whenever possible

Prior concomitant medication includes that given within one month prior to screening. Concomitant medication includes medication given from the Screening Visit until 30 days after the last dose of tisotumab vedotin, or until the patient withdraws consent or starts subsequent anti-cancer therapy, whichever occurs first.

Investigators may prescribe concomitant medications or treatments deemed necessary to provide adequate supportive care except for those medications identified as “excluded” (see Section 9.6.1).

Patients must be instructed not to take any medications, including over-the-counter products, without first consulting the investigator.

Concomitant medication which is ongoing at end of trial of the base protocol should be entered again at the time of signing informed consent (start date should be the original start date).

9.6.1 Excluded Concomitant Medications

The following medications are considered exclusionary during the trial. The sponsor must be notified if a patient receives any of these during the trial.

- Any investigational anti-cancer therapy.
- Drugs and substances known to be strong CYP3A4 and/or P-gp inhibitors (e.g., amiodarone, boceprevir, clarithromycin, conivaptan, grapefruit juice, indinavir, itraconazole, ketoconazole, lopinavir/ritonavir, mibefradil, nefazodone, nelfinavir, posaconazole, saquinavir, telaprevir, telithromycin, verapamil, voriconazole) should not be administered during the trial period.
- Dietary supplements are allowed during the trial period, except when known to be strong CYP3A4 inhibitors as judged by treating physician.

9.7 Treatment Compliance

Tisotumab vedotin will be administered by trial site personnel, who will monitor patient compliance.

10. TRIAL ASSESSMENTS

Trial procedures will be performed as outlined in the Schedule of Activities ([Table 1](#)). A description of the different assessments is provided below.

10.1 Screening Assessments

All screening procedures must be performed within 21 days before the first dose of tisotumab vedotin in the GCT1015-03 trial, except for the CT-scan that may be performed within four weeks. Screening laboratory samples and CT-scan do not need to be repeated if these were performed as part of the base trial within the required timeframes for the current trial. Magnetic resonance imaging can be performed instead of a CT-scan if used in the base trial. The screening evaluations may be carried out over more than one visit. Written informed consent and any locally required privacy act document authorization must be obtained prior to performing any protocol-specific procedures, including screening evaluations.

10.1.1 Demographics

Date of birth (day and month will be anonymized if required by local regulations); ethnicity, race and gender will be recorded in the eCRF.

10.1.2 Medical History

The Medical History recorded in the applicable base protocol will be the Medical History in this trial as well, i.e., no new Medical History will be collected.

10.1.3 Height and Weight

Height (without shoes) must be measured at screening and recorded in the eCRF rounded to nearest centimeter. Body weight (without overcoat and shoes) will be measured at screening and at first treatment visit within a treatment cycle, and will be recorded in the eCRF rounded to nearest kilogram. If body weight is assessed seven days or less before the day of the planned dosing at Day 1, this value can be used.

10.1.4 ECOG Performance Status

The ECOG performance status scale ([Appendix 1](#)) will be used and will be assessed by the investigator at screening.

10.1.5 Neuropathy Assessment

A standard scheme for assessment of peripheral neuropathy will be used at screening. Patients should not be included in this trial if they have CTCAE grade ≥ 2 peripheral neuropathy.

10.1.6 Skin Assessments

Development of skin reactions at the end of the base trial will be assessed at screening of the GCT1015-03 trial. Patients should not be included in this trial if they have ongoing acute or chronic inflammatory skin disease.

10.1.7 Ophthalmological Evaluation

Ophthalmological evaluations should be performed at screening and during the trial as indicated in the trial flow chart.

The ophthalmological evaluation should include collection of medical ophthalmological history (at screening only), visual acuity assessment, Shirmer's test, slit-lamp examination, measurement of ocular pressure and funduscopy.

Patients experiencing ocular symptoms during the trial must be referred to an ophthalmologist for prompt review (preferably within 72 hours and no later than within one week).

10.2 Efficacy Assessments

Investigator assessment of disease control, by CT-scan, will be collected during screening, and during the Treatment Period until disease progression or the EOT Visit, whichever occurs first. At screening, the last CT-scan of the base protocol may be used if it is performed less than four weeks before Cycle 1 Day 1 of the current trial. Assessments every six weeks (at the end of every second cycle), which are consistent with the schedule for standard of care, are recommended (however, based on local standards, disease monitoring can also be as frequent as every four weeks or as infrequent as every 12 weeks). Disease response or progression should be evaluated by the investigator according to the current published RECIST 1.1 ([Eisenhauer et al., 2009](#)) and recorded in the eCRF. Scans may also be sent for an independent, central imaging review. If reduction of target lesions $\geq 30\%$ in size is observed, a repeat CT-scan will be performed after four weeks to confirm the response. In the case of SD, measurements must have met the SD criteria at least once after study entry at a minimum interval (in general not less than six weeks) that is defined in the study protocol.

Patients with prostate cancer must be clinically refractory and resistant to hormone therapy (castration-resistant prostate cancer [CRPC]) as documented by progression, and can be evaluated based on PSA and/or bone metastases according to the Prostate Cancer Working Group Guideline ([Scher et al., 2008](#)). Assessment of bone metastases by radionuclide bone scan every 12 weeks is recommended, but frequency should be based on local standards. If there is suspicion of progression, another bone scan will be performed twelve weeks later. Patients with prostate cancer will be evaluated according to RECIST 1.1 in combination with PSA.

For patients with ovarian cancer, blood samples for CA 125 assessment will be drawn for local analysis. Patients with ovarian cancer will be evaluated according to RECIST 1.1 in combination with CA 125.

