8.2 Schedule of Activities

Table 1: Trial Flow Chart - 1Q3W Treatment Scheme

Procedure	Screening (up to 21 days before Day 1)	Treatment Period Cycle 1 – X (21-day cycle \pm 7 days) Day 1	End-of-Trial Visit (30 days after last dose + 1 week)	Comments
Informed consent	X			
Eligibility criteria	X			
Demography	X			
Height	X			
Weight	X	X		To be taken at screening and at start of each treatment cycle
Pregnancy test	X	X		To be taken at screening and at start of each treatment cycle for women of childbearing potential
Vital signs	X	X		Blood pressure pulse, heart rate and temperature taken at screening and before and after treatment
ECG	X	X		To be taken at screening and before each treatment
ECOG performance status	X			
Neuropathy assessment	X			
Skin assessment	X			
Ophthalmology evaluation	X	X	X	To be performed according to the schedule in the base protocol. Patients experiencing ocular symptoms must be referred to an ophthalmologist for prompt review (preferably within 72 hours and no later than within 1 week).
Laboratory sampling	X	X	X	Local laboratories will be used. Screening laboratory samples do not need to be repeated if performed at the base trial. Details on laboratory samples are provided in Section 10.3.4.

Procedure	Screening (up to 21 days before Day 1)	Treatment Period Cycle 1 – X (21-day cycle \pm 7 days) Day 1	End-of-Trial Visit (30 days after last dose + 1 week)	Comments
Trial drug administration		X		Treatment administration schedule to follow the treatment schedule in the base protocol.
Preventive eye therapy		X		Preventive eye therapy to be administered in relation to infusions as detailed in Section 9.5.4.
Response assessment (CT-scan, PSA, CA 125)	X	X	X	Last CT-scan of base trial to be used at screening if less than 4 weeks old, otherwise a new CT-scan needs to be obtained. Then, to be performed every 6 weeks (at the end of every second cycle) during Treatment Period, and response to be confirmed 4 weeks later. Response assessments will be recorded in the eCRF. PSA will be performed for CRPC patients. CA 125 will be performed for patients with ovarian cancer.
Radionuclide bone scan		X		For patients with CRPC, assessment of bone metastases by radionuclide bone scan every 12 weeks is recommended, but frequency should be based on local standards. If there is suspicion of progression, another bone scan will be performed twelve weeks later.
AE/SAE review	X	X	X	
Concomitant medication	X	X	X	

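### Does Protocol 10.2 need changing because it names no reference scan, no target-lesion carry-over rule and no fixed stable-disease interval, when SAP 10.1 uses the base-trial baseline?

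*Protocol*

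**What the plan says.** Protocol 10.2 has the investigator evaluate response and progression by RECIST 1.1 and enter the result in the eCRF. Six-weekly scans are recommended, but "disease monitoring can also be as frequent as every four weeks or as infrequent as every 12 weeks". Once target lesions have shrunk by at least 30%, "a repeat CT-scan will be performed after four weeks to confirm the response"; Table 1 (Protocol 8.2) likewise has "response to be confirmed 4 weeks later". The only scan singled out at entry is the screening CT: "Last CT-scan of base trial to be used at screening if less than 4 weeks old". Neither place calls that scan, or any other, the reference for the 30%.

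On stable disease, Protocol 10.2 says "measurements must have met the SD criteria at least once after study entry at a minimum interval (in general not less than six weeks" and adds that this interval is one "that is defined in the study protocol". No other section sets it.

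Elsewhere the protocol does carry information over from the base trials. For medical history, "no new Medical History will be collected" (10.1.2). For drugs, "Concomitant medication which is ongoing at end of trial of the base protocol should be entered again at the time of signing informed consent" (9.6). It has no matching sentence for target lesions.

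SAP 10.1 sets the tumor baseline at the latest assessment preceding the first base-trial dose. This overrides the general this-trial baseline in SAP 4.6. SAP 10.1 also brings base-trial local tumor assessments into the listings. Protocol 12.2 and SAP section 4 limit the output to listings, and SAP 13.1 plans no tables.

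**The concern.** Patients enter with stable disease or better, or with partial response or better, from the base trial (Protocol 8.5.1). Their tumor sum at entry will therefore often be below its pre-treatment value. A site that measures change from the screening CT and an analyst who measures it from the base-trial baseline can reach different answers for the same visit. Listing 16.02.02.01 (lesions) and Listing 16.02.02.02 (recorded response) could then disagree. If lesions were chosen afresh at screening, the two sums would not be comparable without matching lesions one by one. The stable-disease sentence has two defects of its own: it is circular about the interval, and scans are permitted every four weeks against a six-week floor. The secondary endpoint, objective response rate, appears to be at stake, as does the trigger for the confirmatory scan.

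**Working it through.** The plan states no figure to reproduce, so the check is whether each silence can alter a planned result. All millimetre values below are assumptions; the 30% and the 4, 6 and 12 weeks are the protocol's.

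**1. Reference scan.** Change = current sum / reference sum - 1. Take 100 mm at base-trial baseline, 80 mm at entry and 68 mm now.
- Against base-trial baseline: 68/100 - 1 = -32%, so the trigger is met.
- Against the entry scan: 68/80 - 1 = -15%, so it is not. The trigger would need 0.7 × 80 = 56 mm.

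More generally, with a base-trial sum of 100, a 30% cut from the entry scan equals a cut from base-trial baseline of 1 - 0.7 × entry/100:

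| Entry sum (assumed) | Equivalent reduction from base-trial baseline |
|---|---|
| 100 | 30% |
| 85 | 40.5% |
| 70 | 51% |
| 60 | 58% |
| 50 | 65% |

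The choice of reference therefore matters in principle. For the analysis, though, SAP 10.1 has already chosen, and the diameters, the base-trial assessments and this trial's first-dose date are all listed (SAP 10.1 and section 4). A reader can compute either change and can separate a response present at entry from a new one.

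**2. Target-lesion set.** Take base-trial lesions 40 + 30 + 30 = 100 mm and entry values 34 + 26 + 24 = 84 mm, a change of -16%. If only the first two were followed, the matched comparison is (34 + 26)/(40 + 30) - 1 = 60/70 - 1 = -14.3%. A figure of 60/100 - 1 = -40% arises only by setting a two-lesion sum against a three-lesion sum, and neither document plans that comparison. SAP 10.1 lists method, location, description and diameters for each target lesion, so a changed set would show in the listing.

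**3. Confirmatory scan.** If the trigger were read from the entry scan and missed, the next scheduled scan comes 4 - 4 = 0, 6 - 4 = 2 or 12 - 4 = 8 weeks later than the repeat CT would have. Stopping treatment does not by itself lose the confirmation, because Table 1 also schedules a response assessment at the End-of-Trial Visit, 30 days after the last dose.

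**4. Stable-disease clock.** A stable scan at week 4 is 6 - 4 = 2 weeks short when counted from Cycle 1 Day 1. Counted from the screening CT it can be as late as about 4 + 4 = 8 weeks. Counted from base-trial first dose it clears six weeks if that dose was at least 2 weeks before entry. So the starting point does change the label, but no planned output uses the label. The endpoint is objective response rate (Protocol section 7), which does not count stable disease. SAP 13.3 contains no best-overall-response or disease-control listing.

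**5. CA 125.** SAP 10.2 requires change from the initial trial's baseline, while the list of imported base-trial data in SAP section 4 omits CA 125. The specific section already gives the instruction, so the omission is clerical.

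**The case for a change.** The strongest reply is that in a listings-only trial the listings are the entire efficacy result, so they should be readable without detective work. The sponsor saw the need for carry-over rules for history and medication and left out the lesions behind the secondary endpoint. Citing RECIST does not say which of two trials supplies the baseline, and the stable-disease sentence refers the reader back to the document that contains it. SAP 4.9 leaves room for summary tables. SAP 10.1 imports only local base-trial assessments while also listing central reads, with no stated reference for the latter. Progression is a reason to stop treatment (Protocol 8.5.3.1), so how sites read scans is not purely an analysis matter.

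Part of this stands. The silences are real, discordant listings are possible, and any ad hoc response table would have to state its reference. It stops short of a change for three reasons.

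- Nothing shows that sites used a different reference. Protocol 10.2 sends them to published RECIST 1.1 and Protocol 13.3 to eCRF Completion Guidelines, which are not available here. The documents leave the matter open without contradicting each other, and this review picks no reading for clinical use.
- Writing down the missing items asks for more detail without offering a better method. A lesion identifier or response flag would ease reading but alter no planned result.
- New protocol sentences mean an amendment. Under Protocol 15.2 that needs submission, and approval unless it is administrative. It could not alter lesions already selected: the first patient entered under Final Protocol 3.0 of July 2017, and the SAP of January 2019 already refers to who is enrolled.

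**Conclusion.** No change follows. Protocol 10.2 is thin on the reference scan and lesion continuity and circular on the stable-disease interval, but these are omissions. None is a stated rule that gives a wrong answer. SAP 10.1 supplies the baseline for the analysis and puts the lesion-level data on the page. With about 25 patients, no hypotheses and no planned tables, the effect on planned results is nil. The possible effect is a visible disagreement between two listings for some patients, whose number cannot be estimated from the documents.

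This rests on three assumptions: base-trial lesion data are available in enough detail to match lesions, listings remain the only planned output, and site instructions do not conflict with SAP 10.1. If a response summary is ever produced under SAP 4.9, the sensible course is to use the SAP 10.1 baseline and footnote any patient whose target set changed. The present plan already allows that.
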